Rescue Therapy: Commercially available preservative free artificial tears (AT) provided by Sponsor are not allowed during the treatment period. Per the investigator's discretion if the patient requires rescue therapy during the 8-week treatment period then they can receive artificial tears provided by the sponsor for up to four times per day. The frequency of rescue therapy must be documented in the patient's diary.

The study will be a total of 34 weeks in duration: a screening period of 2 weeks, followed by 8 weeks of treatment and a 24-week follow-up period. At the end of the screening period (at Visit 2), patients meeting the entry criteria for this study will be assigned to treatment with OXERVATE[™] 0.002% (20

mcg/mL) cenegermin-bkbj ophthalmic solution which will be known as Study Product beginning the morning following Visit 2.

Following the completion of the treatment period, patients will be followed up for an additional 24 weeks (for patients healed and non-healed [and not meeting d/c criteria] at Week 8) and will be evaluated at the end of the follow-up period. At the investigator's discretion, the subject may be seen for an Unscheduled Visit to evaluate for safety. Patients who prematurely discontinue for whatever reason will not be followed post discontinuation and should have Visit 6 assessments completed.

At Visit 1, eligible patients will be instructed to discontinue all topical ophthalmic medications and will only be allowed to use commercially available preservative free tears provided by the sponsor to be used up to four times per day during the screening period. At the conclusion of the Baseline Visit (Visit 2) eligible patients will be dispensed a 2-week supply of Study Product from the onsite freezer in a sealed bag and will be instructed to self-administer the Study Product one drop six times a day starting on the day after Day 0/ Visit 2 through Week 8 of the controlled treatment period according to the dosing schedule shown in Table 1 (Dosing Schedule).

Table 1 Dosing Schedule

TREATMENT	TREATMENT DOSING SCHEDULE*
OXERVATE™ 0.002% (20 mcg/mL) cenegermin-bkbj ophthalmic solution	Morning (8 AM)
	Mid-morning (10 AM)
	Noon (12 PM)
	Early afternoon (2 PM)
	Mid afternoon (4 PM)
	Late afternoon (6 PM)

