Patients who meet the definition of Deterioration or No Improvement in the study eye at week 8 and during the follow up period, will be discontinued from the study and treated as appropriate at the discretion of the investigator.

Deterioration or No Improvement is defined by any of the following:

- In the Study Eye, the FCS is unchanged (Grade=3) from baseline in the qualifying NEI zone.
- At the PIs discretion, in the study eye there is a progression from baseline in the non-qualifying zones
- decrease in BCDVA by >10 ETDRS letters from baseline.
- progression in staining to a PED or corneal melting or perforation
- onset of infection
- Require an ocular surgical procedure, including the need for a corneal transplant.

Note: If there is a deterioration in the non-study eye, the Investigator may discontinue treatment in that eye and initiate alternative treatment at their discretion in the non-study eye, but continue following the study eye per protocol.

[figure not shown]
All patients will attend the following clinic visits in the following sequence:

- Screening (Visit 1/Day -14)
- Baseline and First Study Product Pick-Up (Visit 2/Day 0)
- Product Pick-Up (Visit 3/Week 2)
- Treatment Assessment and Study Product Pick-Up (Visit 4/Week 4)
- Product Pick-Up (Visit 5/Week 6)
- End of 8-week Treatment (Visit 6/Week 8)
- Follow-Up and Final Study Visit (Visit 7/Week 32).

The trial structure for subjects is shown in **Figure 1**

Figure 1 Study Schematic

Any subject who meets the definition of experiencing a deterioration in the study eye, will be discontinued from the study, and followed per the Investigator's discretion.

If there is a deterioration in the non-study eye, the Investigator may discontinue treatment in that eye and initiate alternative treatment at their discretion in the non-study eye, but continue following the study eye per protocol.

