- Adverse Events that caused a decrease in visual acuity of >30 ETDRS letters or > +0.6 LogMAR (compared with the last assessment of visual acuity at the last visit) lasting >1 hour.
- Adverse Events that caused a decrease in visual acuity to the level of Light Perception or worse lasting >1 hour.
- Adverse Events that required surgical intervention (e.g., conventional surgery, vitreous tap or biopsy with intravitreal injection of anti-infectives, or laser or retinal cryopexy with gas) to prevent permanent loss of sight.
- Adverse Events associated with severe intraocular inflammation (i.e., 4+ anterior chamber cell/flare or 4+ vitritis).
- Adverse Events that, in the opinion of the investigator, required medical intervention to prevent permanent loss of sight.

Serious Adverse Event

A Serious Adverse Event (SAE) is defined as any untoward medical occurrence that at any dose:

- results in death,
- is life-threatening (i.e. the patient was at risk of death at the time of the event. It does not refer to an event which hypothetically might have caused death if it were more severe),
- requires inpatient hospitalization or prolongation of existing hospitalization,

NOTE: In general, hospitalization means that the individual remained at the hospital or emergency ward for observation and/or treatment (usually involving an overnight stay) that would not have been appropriate in the physician's office or an out-patient setting. Complications that occur during hospitalization are AEs. If a complication prolongs hospitalization or fulfills any other serious criteria, the event is serious. When in doubt as to whether "hospitalization" occurred, the event should be considered serious.

• results in persistent or significant disability/incapacity,

NOTE: This definition is not intended to include experiences of relatively minor medical significance such as uncomplicated headache, nausea, vomiting, diarrhea, influenza, or accidental trauma (e.g., sprained ankle) which may interfere or prevent everyday life functions, but do not constitute a substantial disruption.

- is a congenital anomaly/birth defect,
- is medically significant or important medical condition, i.e. an important medical event that based upon appropriate medical judgment, may jeopardize the patient, and may require medical or surgical intervention to prevent one of the outcomes listed above.

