1.3.3.3 Best Corrected Distance Visual Acuity (BCDVA)

The logarithm of the minimal angle of resolution (logMAR) visual acuity score (ranged from -0.3 to 1) and Snellen score (ranged from 20/10 - 20/200) will be recorded at Visit 1, 2, 4, 6, 7.

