The improvement in corneal sensitivity, defined as change from baseline > 0 (cm) of the study eye, will be summarized as a binary goal attainment variable (Yes/No).

• Schirmer I change from baseline to weeks 4, 8, and week 32

The Schirmer tear test result (mm) in the study eye will be summarized as a continuous variable.

• TFBUT change from baseline to weeks 4, 8, and week 32

The average TFBUT result (sec) of two repeat measurements in the study eye will be summarized as a continuous variable.

• Mean change in BCDVA from baseline to Week 4, 8, and week 32

The logMAR visual acuity score in the study eye will be summarized as a continuous variable.

Percentage of patients that achieve a 15-letter gain in BCDVA at 4 and 8 weeks.

The patients that achieve a 15-letter gain in BCDVA at 4 and 8 weeks will be determined based on Week 4 or 8 logMAR – Baseline logMAR \leq -0.3. It will be analyzed using a binary goal attainment variable (Yes/No).

• IDEEL change from baseline at week 4, 8, and week 32

Subscores will be derived for the following modules, and will be calculated only if at least 50% of the items of the dimension are completed; otherwise, the scores are missing.

Module 1:

Dry eye impact on daily life (27 questions) comprising 3 QoL domains: 1.a "Daily activities limitations", 1.b "Emotional well being" and 1.c "Work limitations". 26 questions will be considered as part of one of these 3 domains. Question 22 will not be considered part of a domain.

1.a: Daily Activities

| Daily activities section | Used in calculation of domain score? |
|---|---|
| 1. Doing close work in the morning or afternoon (such as crossword puzzles, reading, looking at a computer, and/or sewing) | Yes |
| 2. Doing close work in the evening or at night | Yes |
| 3. Driving | Yes |

Statistical Analysis Plan

| 4. Being around and/or using scented products (such as cologne or hairspray) | Yes |
|--|-----|
| | Yes |
| 5. Working on a computer | |
| 6. Going somewhere where there is tobacco smoke or being | Yes |
| around someone who smokes | |
| 7. Wearing contact lenses | No |
| 8. Wearing make-up near or on my eyes | No |
| 9. Flying on an airplane | No |

| Response for questions 1 to 9 | Original | Item score |
|--|---------------|------------|
| | response code | |
| I did not do this activity for reasons other than | 1 | 5 |
| my dry eyes | | |
| None of the time | 2 | 5 |
| A little of the time | 3 | 4 |
| Some of the time | 4 | 3 |
| Most of the time | 5 | 2 |

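### The acuity-loss AESI is measured only against the last visit, so a loss of more than 30 letters from baseline that builds up over several visits can miss it

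*Protocol*

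**What the plan says.** Protocol 8.1 lists sight-threatening events that count as AESIs and are handled like SAEs; 8.4.1 requires SAE reports within 24 hours. The first is "Adverse Events that caused a decrease in visual acuity of >30 ETDRS letters or > +0.6 LogMAR", measured "compared with the last assessment of visual acuity at the last visit" and lasting more than one hour. The other acuity criterion is absolute: "Adverse Events that caused a decrease in visual acuity to the level of Light Perception or worse lasting >1 hour". The remaining three cover surgical intervention, severe intraocular inflammation, and medical intervention that the investigator judges necessary to prevent permanent loss of sight.

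Elsewhere the protocol measures vision loss from baseline. Deterioration in Protocol 3.3 includes a "decrease in BCDVA by >10 ETDRS letters from baseline" in the study eye. This governs leaving the study and does not make an event an AESI. Its timing is worded in more than one way:

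- One sentence in 3.3 requires discontinuation at Week 8 and during follow-up.
- A later sentence in 3.3, after the study schematic, requires it for any subject with deterioration in the study eye and gives no time limit.
- Protocol 6.2 lists the 10-letter loss, with no stated reference, among reasons for which patients may be discontinued.

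For the non-study eye, 3.3 only allows the investigator to stop treatment in that eye.

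SAP 1.3.3.3 states that acuity "will be recorded at Visit 1, 2, 4, 6, 7". Protocol 3.3 adds that "the subject may be seen for an Unscheduled Visit to evaluate for safety".

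**The concern.** A reference that moves to the latest visit does not add up successive losses. Two eyes with the same total loss from baseline can then be classified differently, depending only on how the loss fell between visits. The criterion exists to bring sight-threatening harm into expedited reporting, and gradual loss can be as sight-threatening as sudden loss. At stake is whether the sponsor hears of such a case within 24 hours or through routine AE collection.

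The analysis does not make up for this. SAP 5.2 handles acuity as mean change and as a 15-letter gain, with no category for loss. SAP 6.1 and the table list contain no AESI summary. Individual values are listed (Listing 16.2.6.3), but only in the final output.

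**Working it through.** **Inputs**
- Limit: more than 30 letters or more than 0.6 logMAR (Protocol 8.1).
- Conversion: SAP 5.2 equates a 15-letter gain with a logMAR change of -0.3, so 0.3 / 15 = 0.02 logMAR per letter.
- Scheduled acuity: Visits 1, 2, 4, 6 and 7, giving three intervals after baseline (2 to 4, 4 to 6, 6 to 7).
- Recorded scale: logMAR -0.3 to 1.0 (SAP 1.3.3.3).
- Discontinuation rule: more than 10 letters lost from baseline, study eye.

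**The plan's own figure.** 30 × 0.02 = 0.60 logMAR. The letter and logMAR forms of the limit agree.

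**Condition for a miss.** Every interval loss is at most 30 letters, and the total from baseline exceeds 30.

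**Largest loss from baseline that misses the criterion, using scheduled visits only**

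| When the 10-letter rule acts | Path | Total |
|---|---|---|
| Every visit | at most 10 letters (otherwise the patient leaves), then 30 | 10 + 30 = 40 letters (0.80 logMAR) |
| Week 8 and follow-up only | 30 by Visit 4, then 30 by Visit 6, where the rule ends participation | 30 + 30 = 60 letters (1.20 logMAR) |
| Not covered (treated non-study eye) | 30 in each of three intervals | 3 × 30 = 90 letters (1.80 logMAR) |

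In the first row the missed range is 31 to 40 letters. From 20/20 (logMAR 0.0), 40 letters gives 20 × 10^0.80, about 20/126.

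**Scale limits.** The recorded scale spans 1.0 - (-0.3) = 1.3 logMAR, or 1.3 / 0.02 = 65 letters, so the 90 in the last row is an arithmetic ceiling that the scale cannot show. Within the scale, a 31-letter loss (0.62) needs a baseline of 0.38 or better, 40 letters needs 1.0 - 0.8 = 0.2 or better, and 60 letters needs 1.0 - 1.2 = -0.2 or better. Also, once the last-visit value is 0.4 or worse, a further loss of more than 0.6 would lie beyond 1.0. A first loss below the limit can therefore put the criterion out of reach for that eye on the recorded scale.

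**Effect of a baseline reference.** Any total above 30 letters meets the limit, however it is split between visits.

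**The case against.** The strongest reply is that the definition is event-based. It speaks of an adverse event that caused a loss lasting more than an hour, so the last visit may mean the last visit before the event began. For one progressive event starting after Visit 2, the reference would then stay at Visit 2 and the losses would add up. Protocol 8.3 also applies SAE procedures once a non-serious event becomes serious. This reading is possible, but 8.1 does not state it, and sites could apply either. It weakens the point to a wording gap without removing it.

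The second reply is that the loss would not go unnoticed. This stands. Protocol 8.2 makes any clinically relevant untoward change in a study parameter an AE. Criteria for investigator judgement, intervention, severe inflammation, hospitalization, disability or light perception may also bring a case into expedited reporting.

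A reader might go further and infer that a fall from 20/20 to 20/200 (50 letters) in steps never meets the criterion. The documents do not support that:

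- Under the untimed sentence in 3.3, a study eye that lost 25 letters by Visit 4 leaves the study, and the second 25 is not reached.
- A split of 35 + 15 does meet the limit. In two steps, 50 letters is missed only if the first step is 20 to 30.
- A 20/20 baseline is itself an assumption, because the acuity wording of inclusion criterion 5 is ambiguous.

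A reader might also infer that closer follow-up always makes the criterion harder to meet. That holds only where acuity is measured at an unscheduled visit. Protocol 6.1.1 asks for vision at each visit, but the schedule has no unscheduled column.

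**Conclusion.** A cheap improvement to safety reporting. On the plain reading of 8.1, cumulative study-eye losses of 31 to 40 letters can miss this AESI if the 10-letter rule acts at every visit, and losses up to 60 letters can be missed if it acts only at Week 8 and in follow-up. A treated non-study eye has no such rule to limit the loss. The gap concerns AESI classification and 24-hour reporting; it does not mean that the loss goes unrecorded.

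The bounds assume whole-letter losses, acuity at scheduled visits only, and a last-visit reference that moves during a continuing event. An extra acuity measurement during treatment could raise the 60, but not the 40.

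Two further inferences are unsupported. The different references in 8.1 and 3.3 are not a contradiction, since one governs reporting and the other discontinuation. Nor can an effect on the serious-event rate be stated: the documents give no probability for such a case and do not describe stepwise loss as the usual course. The 35 planned evaluable patients are completers, whereas SAP 6 summarises safety in the FAS.

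**What to change.** In Protocol 8.1, keep both limits and replace the reference with: *compared with baseline (Visit 2) or with the last assessment before the event, whichever shows the larger loss*. Apply it to the letter and logMAR forms alike. Sudden loss is still caught, and an event before Visit 2 is still judged against the last assessment before it.

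The cost is one phrase in an amendment under Protocol 12.4 and possibly a few more 24-hour reports. No assessment is added, because acuity is already measured in both eyes at the visits needed.

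Separately, the timing and force of discontinuation for acuity loss in Protocol 3.3 (two sentences) and 6.2 must be reconciled. The size of the gap depends on the outcome, but the change to 8.1 is useful under either wording.

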8.2. MONITORING FOR ADVERSE EVENTS

At each visit following study informed consent form signature, after the subject has had the opportunity to spontaneously mention any problems, the Investigator or appropriate designee should inquire about AEs by asking the standard questions:

- "Have you had any health problems since your last study visit?"
- "Have there been any changes in the medicines you take since your last study visit?"

AEs should be reported for any clinically relevant change in concomitant condition(s) that is the result of an untoward (unfavorable and unintended) change in a subject's medical health. Anticipated day-to-day fluctuations of preexisting conditions that do not represent a clinically significant exacerbation or worsening need not be reported as AEs. Changes in any protocol-specific [ocular or] systemic parameter evaluated during the study are to be reviewed by the Investigator. In addition, the subject's responses to any questionnaire utilized during the study are to be reviewed by the Investigator. Any untoward (unfavorable and unintended) change in a protocol-specific parameter or questionnaire response that is clinically relevant is to be reported as an AE. These clinically relevant changes will be reported regardless of causality.

8.3. RECORDING

AEs will be collected and recorded for any untoward event that occurs in a patient from the time he or she signs the ICF for the trial until 24 weeks after the last dose of Study Product. Thus, any untoward medical occurrences or unfavorable and unintended signs, symptoms, or diseases that occur in the pretreatment, treatment, or post treatment period are to be considered AEs and/or SAEs, and consequently recorded and reported as such. Should a non-serious AE become serious, the Investigator will then follow the same reporting procedures as for SAEs.

Each AE will be described by:

- Its duration (start and stop dates)
- Severity
- Its relationship to the study drug; (suspected/unsuspected)
- Action(s) taken
- Outcome

Medical conditions/diseases, or cancer related signs/symptoms present before starting study treatment shall be documented in the medical history section of the CRF; these conditions are considered AEs only if they increase either in frequency or severity once informed consent has been signed.

8.3.1. Follow-Up of patients with Adverse Events

The Investigator is responsible for adequate and safe medical care of patients during the trial and for ensuring that appropriate medical care and relevant follow-up procedures are maintained after the trial. All AEs should be followed-up to determine outcome of the reaction. The Investigator should follow up the event until resolution or stabilization of the condition. It is the Investigator's responsibility to assure that the patients experiencing AEs receive definite treatment for any AE, if required.

If subject was hospitalized due to a SAE, a copy of the discharge summary is to be forwarded to the Sponsor as soon as it becomes available. In addition, a letter from the Investigator that summarizes the events related to the case as well as results of any relevant laboratory tests also may be requested. Further, depending upon the nature of the SAE, Dompé may request copies of applicable segments of the patient's medical records. In case of death, a copy of the autopsy report, if performed, should also be provided.

The Investigator shall inform the Sponsor with an appropriate written communication, whenever he/she becomes aware of new available information regarding the SAE once the condition is resolved or stabilized and when no more information about the event is expected. Additional information received after the initial SAE has been reported to the Sponsor should be reported as follow-up information following the same procedure and timeline as the initial SAE.

For pharmacovigilance purposes, all SAEs should be followed-up to clarify as completely as possible their nature and/or causality and until all queries have been resolved. All SAEs will be followed up until the events resolve or the events or sequelae stabilize, or it is unlikely that any additional information can be obtained after demonstration of due diligence with follow-up efforts (i.e. subject or Investigator is unable to provide additional information, or the subject is lost to follow up), unless subject has withdrawn his/her consent.

8.3.2. Relationship of AEs to the Study Product

The Investigator will assess the possible relationship between the AE and the investigational medication, according to the criteria in **Table** below:

Relationship of the Adverse Event to the Study Product

None (Intercurrent Event)	An event that is not and cannot be related to the Study Product, e.g. patient is a passenger in a road traffic accident.	
Unlikely (remote)	Relationship is not likely e.g. a clinical event including laboratory test abnormality with temporal relationship to drug administration which makes a causal relationship improbable and in which other drugs, chemicals or underlying disease provide more plausible explanations	
Possible	Relationship may exist, but could have been produced by the patient's condition or treatment or other cause	
Probable	Relationship is likely, the AE abates upon discontinuation of Study Product and cannot be due to the patient's condition	
Highly Probable	Strong relationship, the event abates upon discontinuation of l Study Product and, if applicable, re-appears upon repeat exposure	

8.3.3. Severity of AEs

The Investigator will grade the severity of any AE using the definitions in the **Table** below. For each episode, the highest severity grade attained should be reported.

Severity of the Adverse Event

Mild	Grade 1 - Does not interfere with patient's usual function (awareness of symptoms or signs, but easily tolerated [acceptable]).	
Moderate	Grade 2 - Interferes to some extent with patient's usual function (enough discomfort to interfere with usual activity [disturbing]).	
Severe	Grade 3 - Interferes significantly with patient's usual function (incapacity to work or to do usual activities [unacceptable])	

8.4. SERIOUS ADVERSE EVENT REPORTING

8.4.1. Reporting Procedure for Investigators to Lexitas Pharma Services, Inc. And Dompé Drug Safety

The Investigator must report all SAEs, regardless of presumed causal relationship, to *Lexitas Pharma Services, Inc.* Pharmacovigilance and to Dompé Drug Safety, by e-mail (preferred) or fax within 24 hours of learning of the event.

SAE reporting should be sent to:

SAE Email address: [contact]

Dompé Drug Safety: [contact]

Dompé Drug Safety: [name]

In case of failure of/lack of access to email, or fax, the event should be reported using the SAE hotline [contact]**.

If an SAE is reported via telephone, the telephone report should be followed by a written report using a reporting method described above (i.e., completion of paper form).

The investigator should also report information on SAEs that continue after patient has completed his/her participation in the study (whether study completion or withdrawal) unless patient has withdrawn his/her consent.

Information on SAEs will be recorded on the SAE form approved by the Sponsor. Additional follow-up information (e.g., test results, autopsy, and discharge summary) may be requested to supplement the SAE report form and can be attached as de-identified records. Follow-up reports (as many as required) should be completed and e-mailed/faxed following the same procedure and timeline above, marking the SAE form as "follow up Number XX".

Whenever more than one SAE is observed, the Investigator should identify which is the primary serious adverse event, i.e. the most relevant one. In any case, the Investigator is requested to record his/her opinion about the relatedness of the observed event(s) with the investigational medication.

In line with CT3 Detailed Guidance and ICH E2A provisions, although the Investigator does not usually need to actively monitor patients for AEs once the trial has ended, if the Investigator becomes aware of a SAE occurring to a patient after that patient has ended his/her participation in the study (whether study completion or withdrawal), the SAE should be reported by the Investigator to the Dompé/Lexitas Pharmacovigilance. Such "post-study cases" should be regarded for expedited reporting purposes as though they were study reports. Therefore, a causality assessment and determination of expectedness are needed for a decision on whether expedited reporting is required.

